4.1.5.2. Secondary outcomes to be evaluated

- To determine the time to deterioration in two or more points of the 7-point ordinal scale in the two study groups.
- To determine the clinical state, using the 7-point ordinal scale, on days 2, 5, 8, 11, 15, and 21.
- The proportion of subjects requiring hospitalization, use of supplemental oxygen > 24 hours, admission to the ICU, or dying within 21 days in the two trial groups.
- The duration of supplemental oxygen in each arm of the study.
- The duration of hospitalization in each arm of the study.
- The duration of stay in the ICU in each arm of the study.
- The duration of fever (axillary temperature > 38C or subjective feeling of fever) in each arm of the study.
- Proportion of subjects who develop adverse events associated with the study drug.
- Proportion of subjects who required discontinuation of medication due to adverse events.

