4.3.3 Table of visits and follow-ups

| Visit number (V) | Screening | Randomization | Phone call 1 | Phone call 1 | Phone call 1 | Phone call 1 | Phone call 1 | Phone call 1 | Phone call 1 | Phone call 1 |
|---|------------|---------------|-----------------|-----------------|-----------------|-----------------|-----------------|-----------------|-----------------|-----------------|
| Study deadlines | SCR | D1 | D2 | D3 | D4 | D5 | D8 | D11 | D 15 | D 21 |
| Intervals (days) | | | | | | | ±1 | ±1 | ±1 | ±1 |
| Signed informed consent form | X | | | | | | | | | |
| Inclusion/exclusion criteria | X | X | | | | | | | | |
| Assignment of the research participant number | X | | | | | | | | | |
| Demographic Data | X | | | | | | | | | |
| Medical background check | | X | | | | | | | | |
| Weight | X | | | | | | | | | |
| Vital signs and pulse oximetry | | X | | | | | | | | |
| Calculation of NEWS -2 score: | | X | | | | | | | | |
| Collection of clinical data | | X | | | | | | | | |
| Urine sample to evaluate pregnancy | X | | | | | | | | | |

| | | | | | | | | | | |
|---|-----------------------|----------|----------|----------|----------|----------|----------|----------|----------|----------|
| Blood Sample to evaluate Hepatic enzymes ² | X ² | | | | | | | | | |
| Randomization | | X | | | | | | | | |
| Dispensing and initiating medication/placebo | | X | | | | | | | | |
| Evaluation of the 7-point ordinal scale | | X | X | X | X | X | X | X | X | X |
| Assessment of secondary outcomes - Pt. at home or hospitalized? - Has required oxygen? - Has required ICU? - Vital status - Persists with fever? | | X | X | | | X | X | X | X | X |
| Collection of Serious Adverse Events (SAE) | | | X | | | X | X | X | X | X |
| Pharmacotherapeutic Adherence | | X | | | | X | | | | |
| Remember the need to take the investigation product | | | X | X | X | X | | | | |
| Collect symptoms reported to the admin of the investigation product | | | X | X | X | X | X | X | X | X |
| Record of completion | | | | | | | | | | X |

¹ In the case of hospitalized research participants, the study staff will personally visit the subject and/or contact the physician in charge by telephone, and/or through the medical history will obtain the necessary information and thus be able to determine primary or secondary outcomes

² It will not be necessary to collect the liver enzyme sample if there is a recent result no more than 3 days prior to selection.

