4.3.7 Measurement of Security Parameters

On the day of the screening visit, all participants will have their liver enzymes measured. The research participant will not be randomized and therefore will not be included in the study if these are elevated > 1.5 times normal values.

In follow-up calls (days 2, 3, 4, 5, 8, 11, 15, and 21), research participants will be asked about symptoms that have historically been reported in subjects receiving ivermectin (uncontrollable shaking of a body part, dizziness, loss of appetite, nausea, vomiting, stomach pain or bloating, diarrhea, constipation, weakness, drowsiness, chest discomfort, swelling (face, arms, hands, feet, ankles, or lower legs), and other symptoms, pain and swelling in joints, painful and swollen glands in the neck, armpit, or groin, fast heartbeat, eye pain, blurred vision, redness or tearing, swelling (face, arms, hands, feet, ankles or calves), pain and swelling in the joints, painful and swollen glands in the neck, armpit or groin, fast heartbeat, pain in the eyes, blurred vision, redness or tearing, swelling of the eyes or eyelids, abnormal

sensation in the eyes, fever, blisters or peeling of skin, rash, hives, and itching) to complete the information requested by the data collection form. The proportion of research participants with adverse events in both arms will be compared.

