4.4 Sample size

According to the literature and previous data in this study, 75% of the subjects will have the event of interest (disappearance of symptoms) by day 21. Thus, including 390 subjects, we will identify 290 events of interest. With this sample size we will have a power of 80% and an Alpha of 0.05 to detect a Hazard ratio of 1.4 of ivermectin vs. placebo in time to symptom resolution. Taking into account a 2 % follow-up loss and 76 subjects who will be excluded from the primary analysis¹, we will include a total of 476 subjects in the study.

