4.5 Data analysis

An interim analysis will be conducted without breaking the blind when 200 research participants have been randomized. The study will be discontinued if this analysis detects a significant treatment effect on the main objective, if it is detected that a significantly larger group of subjects withdraw from the intervention arm due to adverse events, or if no difference is detected between the two groups. Recruitment will continue while this analysis is performed.

The information will be analyzed with Stata version 14 (SE; Stata corporation, College Station, Texas). For this purpose, subjects will be grouped into 2 groups that comprise

- Group 1:** Subjects who received ivermectin
- Group 2:** Subjects who received placebo.

The baseline characteristics of the subjects will be described by descriptive analysis.

The main analysis will be by intent-to-treat. The time until the disappearance of symptoms will be determined when all research subjects reach day 21. Clinical deterioration or death before the 21st will be right censored- on the 21st. Deaths will be included unless there is strong evidence that the cause of death was not associated with COVID-19. The time until the disappearance of symptoms will be presented in a Kaplan-Meier curve and will be compared with the log-rank test. Hazard Ratios will be calculated with their 95% confidence interval through a Cox proportional-hazards model.

¹ 76 subjects included in the study had errors in the enlistment of the investigation product consecutively for three weeks, and will be excluded from the primary analysis.

Secondary outcomes and adverse events in each of the groups will be expressed by absolute and relative frequencies with their corresponding 95% confidence interval. For the univariate analysis in the quantitative variables, statistical parameters of central tendency and dispersion (means and standard deviations) will be described if the variable has a normal distribution. In case of not having a normal distribution, medians and interquartile ranges will be described. The qualitative variables will be measured and analyzed through proportions with their corresponding 95% confidence interval.

To determine the efficacy of the intervention in secondary outcomes, a bivariate analysis will be performed, evaluating the association of treatment, demographic and clinical variables with the different outcomes.

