4.2. Secondary outcomes

-Proportion of cases with deterioration in two or more points of the 8-point ordinal scale in the two study groups. Proportion of subject who reported an increase in disease severity of 2 or more points on the 8-point ordinal scale relative to the randomization visit.

-Proportion of cases that required hospitalization, use of supplemental oxygen > 24 hours, and admission to the ICU.

-Duration of hospitalization, use of supplemental oxygen and duration of stay in ICU in each arm of the study.

-Clinical state, using the 8-point ordinal scale, on days 2, 5, 8, 11, 15, and 21.

-Proportion of cases who develop fever (axillary temperature > 38°C or subjective feeling of fever) in each arm of the study and duration of fever. Number of days from the randomization visit to an axillary temperature <38°C.

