6.2. Secondary outcomes

Secondary outcomes, hospitalization requirement, ICU or oxygen supplementation and deterioration in more than two points on the scale of clinical results will be analyzed through a Kaplan Meier estimate. Hazard ratio will be estimated by Cox proportional-hazard model. In addition, a logistic regression model in which each secondary outcome will be considered as the dependent variable (1: Event, 0: No event) and the intervention groups as the independent variable (1: ivermectin, 0: Placebo) will be used.

For each outcome, the odds ratio (OR) and its respective 95% CI will be reported. An OR > 1 is indicating favorable results in favor of placebo and an OR <1 in favor of ivermectin. In case of low frequency of individual outcomes, a combined variable will be created using need for hospitalization (general floor or ICU) and need for oxygen (by nasal cannula or mechanical ventilation) and will be analyzed using a logistic regression model reporting the OR with its 95% CI.

Evaluation of the effect of the treatment in each study visit using the 8-point ordinal scale will be estimated using the proportional OR with its respective 95% CI with an ordinal logistic regression. In this step, the 8-point ordinal scale will be inverted in its score, where 0 will correspond to death and 7 to a subject without symptoms. Thus, a proportional OR > 1 will indicate an effect in favor of ivermectin. The 95% confidence interval of the median difference in duration of fever and length of hospitalization or oxygen use will be estimated by bootstrap estimators.

6.3. Sensitivity Analysis and Modification of the Effect for the Primary outcome.

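### Fever duration is compared between arms only by a bootstrap interval for the difference in medians, which at a moderate effect is far less sensitive than a log-rank/Cox analysis of the same records

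*Supplement*

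**What the plan says.** The protocol lists as a secondary outcome "The duration of fever (axillary temperature > 38C or subjective feeling of fever) in each arm of the study". SAP 4.2 turns this into a time: "Number of days from the randomization visit to an axillary temperature <38°C". It also lists the proportion of patients who develop fever.

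SAP 6.2 assigns Kaplan-Meier and Cox to "hospitalization requirement, ICU or oxygen supplementation and deterioration in more than two points on the scale of clinical results". Fever is not in that list. The duration outcomes get this sentence instead: "The 95% confidence interval of the median difference in duration of fever and length of hospitalization or oxygen use will be estimated by bootstrap estimators".

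On recording, the protocol's visit table (4.3.3) asks "Persists with fever" at randomization (D1) and on D2, D5, D8, D11, D15 and D21. Protocol 4.3.7 adds a second source: "In follow-up calls (days 2, 3, 4, 5, 8, 11, 15, and 21), research participants will be asked about symptoms", and fever is on that symptom list. Neither document says whether the date on which fever ended is taken between calls.

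Protocol 4.5 also says: "To determine the efficacy of the intervention in secondary outcomes, a bivariate analysis will be performed". It names no test, scale or censoring rule. SAP 6.5 says secondary outcomes are not imputed, and gives no rule for fever still present at D21 or for death before fever resolves.

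**The concern.** A time to an event is being compared at one point of its distribution, the 50th percentile, while the rest of the curve goes unused. When times are known only to the nearest call, the median of each arm moves in steps, and small or moderate differences can vanish between two calls. The plan already has a method that uses the whole curve and handles censoring, but does not apply it here.

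At stake is the reading of a null result. The amendment log gives fever duration as an indirect marker of antiviral activity. If the interval includes zero almost whatever a moderate effect does, its including zero says little about the drug.

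**Working it through.** **1. The plan's own figures.** The documents give no sample-size figure for fever. For the primary outcome the protocol states "power of 80% and an Alpha of 0.05 to detect a Hazard ratio of 1.4" with 290 events.
- Power with 290 events: √290/2 × ln 1.4 − 1.96 = 2.865 − 1.96 = 0.905, which is 81.7%.
- Events: 390 × 0.75 = 292.5.
- Total: 390/0.98 + 76 = 474, against 476 stated.

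The stated design is reproduced. HR 1.4 is borrowed from it below as a moderate effect.

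**2. Assumptions for fever (not in the documents).** 50, 100 or 200 febrile patients per arm; placebo median fever 2 to 7 days; exponential durations; HR 1.4, and larger values as a check.

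**3. What the grid does to a median.** Counted from randomization on D1, the scheduled days D2, D5 and D8 lie at 1, 4 and 7 days.
- Placebo median 3 days: the ivermectin median is 3/1.4 = 2.14. Both lie between 1 and 4, both are recorded as 4, and the difference is 0.
- Placebo median 5 days: the ivermectin median is 5/1.4 = 3.57. These are recorded as 7 and 4, a difference of 3 days.

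So the result depends on where the medians fall between calls.

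**4. What the median loses even without a grid.** For exponential times the standard error of a sample median is m/(ln 2 × √n). With n = 100 per arm and HR 1.4, m cancels:
- z = (1 − 1/1.4) × ln 2 × 10 / √(1 + 1/1.4²) = 1.980/1.229 = 1.61.
- Power is Φ(1.61 − 1.96), about 36%.

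Log-rank, if nearly all fevers resolve by D21 (200 events): √200/2 × 0.3365 − 1.96 = 0.42, about 66%. With 100 events (50 per arm): 1.68 − 1.96 = −0.28, about 39%.

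**5. Simulation with recorded days.** 100 febrile per arm, HR 1.4, medians 2 to 7 days; percentile bootstrap interval against a two-sided 5% log-rank test on the same recorded data:

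| Fever recorded on | Median interval excludes 0 |
|---|---|
| D2, D5, D8, D11, D15, D21 | 0-3% |
| the same plus D3, D4 | 2-13% |
| every day | 1-26% |

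Log-rank detects the effect in about 60-67%. A separate run of 400 trials per scenario gave 0-6% against 56-65% on the scheduled days. There, log-rank power was 33-39% with 50 febrile per arm and 89-90% with 200, against 0-4% and 0-13% for the interval.

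**6. How often the result is exactly zero.** On the scheduled days at HR 1.4 the estimated difference is exactly 0 in 90-100% of trials at medians of 2-3 days, but in only 13-48% at 4-7 days. With 100 per arm, intervals of exactly [0, 0] were frequent (31-58% in one run, 54-64% in another) only at medians of 2-3 days on those days. With D3 and D4 or daily data they occurred in at most 1%.

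**7. Validity and larger effects.** With no effect the interval excluded zero in 0-3% of runs, below the nominal 5%. Its coverage of the median difference in the recorded data was 90-100%. At HR 2.0 with 100 per arm it excluded zero in 15-84% with D3 and D4 or daily recording. Over 50 to 200 per arm it did so in 0-64% on the scheduled days.

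**The case against.** The best defence has four parts.

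- **The true grid is unknown.** Fever is on the symptom list asked at every call, hospitalized patients' data come from the record, and an end date might be asked at the next call. This stands as a limit on the near-zero figures. It does not remove the loss: with dates known to the day the interval still excludes zero in only 1-26%.
- **Power is not the only yardstick.** The SAP plans an estimate in days, which clinicians read easily, and the simulations use proportional hazards, which favour log-rank. This stands as a reason to keep the interval in days, but not to make it the sole comparison.
- **Fever has other analyses.** The SAP's change summary names the proportion who develop fever as the antiviral marker, and the logistic model in 6.2 can cover it. That answers a different question from duration. The bivariate analysis in protocol 4.5 is too undefined to fill the gap.
- **Censoring matters little to a median** while fewer than half are unresolved and loss is about 2%. This is fair, so the missing D21 rule is a minor part of the point.

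A reader might go further and infer that the difference will almost always appear as zero, that a null result is nearly guaranteed, or that the interval is invalid. The documents do not support this. They give neither the number febrile nor the length of fever. Exact zeros dominate only with a short median on the coarse grid, larger effects can be detected, and the interval errs towards caution.

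**Conclusion.** The point holds as an inefficient choice of analysis for one secondary outcome. At HR 1.4 with 100 febrile per arm, moving from the median interval to log-rank raises the chance of detecting a real effect from at most about a quarter, and from 3% or less on the scheduled days, to about 60-67%. The size rests on assumed numbers febrile, exponential durations and medians of 2 to 7 days. With 50 febrile per arm neither analysis is strong, since log-rank reaches only about one in three. The primary outcome and its conclusion are not touched.

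**What to change.** In SAP 6.2, name time to fever resolution among patients febrile at randomization as the main between-arm comparison of fever duration. Use Kaplan-Meier curves, the log-rank test and a Cox rate ratio with 95% CI. Censor patients still febrile at D21 at that day and patients lost at last contact. Keep patients who die in the risk set to D21 as not resolved. State which record supplies the day of resolution: the scheduled fever item, the symptom list or a reported end date.

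Keep the median difference and its bootstrap interval as a descriptive result in days, and keep the proportion who develop fever to cover fever that starts after randomization.

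The cost is a few sentences in the SAP and one more run of a model already in use, on data already collected. The downsides are a main effect expressed as a rate ratio rather than in days, and a defined febrile-at-entry analysis set that the SAP does not now have.

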5.2. Subgroups

No subgroup analysis will be done.

6. Analysis plan

Initially, all the variables will be described according to the intervention groups in the ITT population. Variables with a normal distribution will be summarized with mean and standard deviation (SD), otherwise, they will be shown with median and interquartile range (IQR). Normal distribution assumption will be evaluated using the Shapiro Wilk test. All analyzes will be done in Stata 16.0® (StataCorp, College Station, Texas, USA).

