The analysis of the primary outcome will be repeated using the population under the per protocol approach and will be considered as sensitivity analysis. Additionally, if differences are found between the research product and the outcomes, it will be evaluated whether variables such as enrollment score on the 8-point scale, duration of symptoms before enrollment, comorbidities, age and sex, modify the effect of the intervention groups, using a multivariate Cox proportional hazards model. This will be done by including interaction terms to the model between the possible modifying variable and the intervention groups. A p value <0.10 will be considered as a possible modifying effect, and a p value <0.05 will be considered as a cut-off point to confirm a significant interaction and therefore, to estimate the effect of the treatment groups with their respective 95% CI.

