6.4. Safety analysis

This analysis will be carried out on an exploratory basis and the frequency and detailed description of each adverse event will be reported.

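### After a positive result, SAP 6.3 lets any one of at least five unadjusted interaction tests count as confirmed effect modification, with about a 23% chance of a false one

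*Supplement*

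**What the plan says.** The text is in SAP (PAE 1.0) section 6.3, after the per-protocol sensitivity analysis. The step is conditional and opens: "if differences are found between the research product and the outcomes, it will be evaluated whether variables". The candidates are "variables such as enrollment score on the 8-point scale, duration of symptoms before enrollment, comorbidities, age and sex, modify the effect of the intervention groups". On method, the SAP specifies a Cox model and adds: "This will be done by including interaction terms to the model between the possible modifying variable and the intervention groups".

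Two thresholds follow. The lower tier is "A p value <0.10 will be considered as a possible modifying effect". The upper tier is "a p value <0.05 will be considered as a cut-off point to confirm a significant interaction", and passing it is the stated reason for going on to estimate treatment effects with 95% CIs.

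Two other sections bear on this. Section 5.2 states: "No subgroup analysis will be done". Section 6.4, on safety, states: "This analysis will be carried out on an exploratory basis". Section 6.3 carries no such label, and neither the protocol nor the SAP adjusts the interaction tests for their number.

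**The concern.** Section 6.3 is a decision rule. One p value below 0.05, from any of five or more tests, is enough to declare a modifier. The list is open, because the five variables are given as examples, and comorbidities could enter as one variable or several. The number of tests is therefore at least five and is not fixed in advance.

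The condition that a difference must first be found does not remove the problem. It is met mainly when the trial is positive, which is when readers would ask who benefits most. A trial of a uniformly effective drug could then report, as confirmed, that the drug works differently by age, sex, symptom duration or baseline score, when only chance was at work.

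**Working it through.** **Inputs from the documents**
- Five named candidates; thresholds 0.05 and 0.10 per test (SAP 6.3).
- Hazard ratio 1.4, power 80%, alpha 0.05, 390 subjects, 290 events, 75% resolved by day 21, 2% loss (SAP 2.2; protocol 4.4).

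**Assumptions**
- Alpha is two-sided.
- The condition in 6.3 refers to the primary test. The SAP says outcomes, in the plural, and names no test.
- There is no true interaction.
- The correlation between the tests is unknown, so a range is shown.

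**1. The plan's own figure.** This matters because power fixes how often the condition is met.
- Freedman: (1.960 + 0.842)² × (2.4/0.4)² = 283 events.
- Schoenfeld: 4 × (1.960 + 0.842)² / (ln 1.4)² = 278 events.
- Power with 290 events: Φ(√290/2 × ln 1.4 − 1.960) = 0.817.
- Events: 390 × 0.75 = 292.5.

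The stated 290 events and 80% power are reproduced closely. One-sided versions (219 and 223 events) do not fit. At the design effect the condition is met about 80% of the time.

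**2. At least one false positive among k tests.** For independent tests this is 1 − (1 − α)^k.

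| Five tests | Independent | Correlation 0.2 | Correlation 0.5 |
|---|---|---|---|
| p < 0.05 | 22.6% | 21.9% | 18.3% |
| p < 0.10 | 41.0% | 39.5% | 33.1% |

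The correlated figures come from 400,000 draws of equally correlated normal statistics. If the open list grew, the independent rate at 0.05 would be 26.5% for six tests, 33.7% for eight and 40.1% for ten.

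**3. Allowing for the condition.**
- Design effect, independent tests: 0.80 × 22.6% = 18.1%.
- Design effect, correlation 0.5: 0.80 × 18.3% = 14.6%.
- No drug effect: 0.05 × 22.6% = 1.1%.

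**4. Simulation check.** Trials of 398 subjects (390/0.98), about 300 events, uniform hazard ratio 1.4, five baseline variables and no interaction were generated, 1,500 per setting. Modifier prevalences and prognostic effects were assumed.

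| Correlation of the variables | Condition met | False modifier given condition (one joint model / separate models) | Overall (joint / separate) |
|---|---|---|---|
| 0 | 79.5% | 25.7% / 26.0% | 20.4% / 20.7% |
| 0.3 | 80.1% | 24.5% / 22.9% | 19.6% / 18.3% |

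A separate run of the same kind gave 80.2%, 25.5% and 20.5% (joint model). With hazard ratio 1.0 the condition was met in 4.7% of trials and the overall rate was 1.2%. The 25.5% rests on about 1,203 trials, so its Monte Carlo 95% interval is roughly 23% to 28%. The small excess over 22.6% should not be interpreted.

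**5. Strength of a single interaction result.** For an evenly split modifier and 290 events, the standard error of the interaction log hazard ratio is about 4/√290 = 0.235. A true ratio of hazard ratios of 1.4 would be detected with power Φ(ln 1.4/0.235 − 1.960), about 30%. Power of 80% needs a ratio near exp(2.80 × 0.235) = 1.9. So a false declaration somewhere among the five (about 23%) is nearly as likely as detecting one real modifier of that size.

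**The case against.** The method in 6.3 is better than many. Most candidates are named in advance, they are tested by formal interaction terms and not by comparing p values within groups, and the tests run only after an overall difference. Leaving secondary interaction tests unadjusted is common. The verb in the upper tier may mean no more than statistically significant, particularly in a translated document. All of this is fair, and it limits the point to an interpretive risk. It does not remove it: the rule still turns one unadjusted result into a declaration, and the SAP uses an exploratory label elsewhere but not here.

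Three stronger readings are tempting, and the documents do not support them.
- A reader might infer that the false-positive rate of about one in four or five applies to any trial run under this plan. It does not: the condition keeps the rate near 1% when the drug has no effect, provided that it refers to the primary test.
- A reader might infer that a chance interaction could restrict or redirect the primary conclusion to a subgroup. No section says so. Section 6.1 fixes the overall log-rank comparison as the main analysis, and 6.3 provides only for further estimates.
- A reader might see a flat contradiction between 5.2 and 6.3. Interaction terms fitted in the whole sample are often distinguished from subgroup analysis, and 6.3 does not say outright that the resulting estimates are modifier-specific, although that is the natural reading. The two sections fit poorly and need a cross-reference; that is as far as the text goes.

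**Conclusion.** The point holds as a conditional one. For a drug that works equally in everyone, five roughly independent tests give about a 23% chance of at least one false declaration once the condition is met, falling to about 18% at correlation 0.5 and rising if the list grows. Overall, at the design effect, the rate is about 18–21% for tests that are independent or modestly correlated, and about 15% at correlation 0.5.

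These figures assume that the condition refers to the primary test and that exactly five tests are done. The closed-form 22.6% does not depend on the simulated prevalences or prognostic effects. If a difference on a secondary outcome could also open the step, the figure of about 1% for an ineffective drug would be too low; the documents do not allow that to be quantified.

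The primary comparison's type I error is untouched. What is at stake is how a positive result would be read, and a change of wording is proportionate to that.

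**What to change.** In SAP 6.3:
- Close the list at the five named variables and state how comorbidities are coded, so that the number of tests is fixed.
- Replace the two-tier 0.10/0.05 rule and the language of confirmation with a statement that the interaction analyses are exploratory and hypothesis-generating.
- Report every interaction estimate with its 95% CI, whatever its p value.
- Only if a significance claim is kept, base it on a multiplicity-controlled test, for example one joint test of the interaction terms or Holm across the five. For scale, a Bonferroni threshold of 0.01 over five independent tests gives a family-wise rate of 4.9%. Whether to keep such a claim is a trade-off, since adjustment lowers power that is already small.

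In SAP 5.2, add a cross-reference saying that any modifier-specific estimates are those from 6.3 and are exploratory.

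The cost is SAP wording only, with no new data and no change to the primary analysis. The downside is that no single interaction could be called confirmed at an unadjusted 0.05.
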